8.4.2 DEFINITION OF DOSE-LIMITING TOXICITIES

A dose-limiting toxicity (DLT) is defined as an adverse event or abnormal laboratory value assessed as unrelated to disease, disease progression, inter-current illness, or concomitant medications and at least possibly related to the study therapy and that occurs within the first 28 days of study therapy. The investigator must notify the Sponsor immediately of any DLTs.

For patients in Arm A receiving mRNA-2416, the following toxicities will be considered a DLT:

- All Grade 3 AEs with the exception of the following:
 - Grade 3 thrombocytopenia lasting <7 days
 - Grade 3 neutropenia without fever or lasting <7 days
- Any Grade 4 or Grade 5 toxicity. Death due to disease progression is not considered a DLT.

For patients in Arm B receiving mRNA-2416 in combination with durvalumab, the following toxicities will be considered a DLT:

Adverse Event (AE)+C2:F16	DLT Criteria		
	Grade 2 Events	Grade 3 Events	Grade 4 events
Diarrhea/colitis	none	Events that do not resolve to Grade 1 or baseline within 14 d (whether or not it is immune-mediated)	DLT
Pneumonitis	Non-infectious pneumonitis that does not resolve to Grade ≤1 within 10 days	Non-infectious pneumonitis is a DLT	DLT
Hepatitis	none	Alanine aminotransferase (ALT) or aspartate aminotransferase (AST) >8×ULN or total bilirubin (TBL) >5×ULN OR events meeting Hy's Law (AST or ALT ≥3×ULN with concurrent increase in TBL ≥2×ULN without evidence of cholestasis or alternative explanations)	DLT
Rash	Any grade rash with bullous formation.	Rash not resolving to Grade 1 or baseline within 30d. Any rash with bullous formation.	DLT
Peripheral neuromotor syndromes such as Guillain-Barre or myasthenia gravis	Events not resolving to Grade 1 within 30d. Events with any signs of respiratory insufficiency or autonomic instability.	Events that do not resolve to Grade 1 within 30d. Events with any signs of respiratory insufficiency or autonomic instability.	DLT
Myocarditis	Events that do not resolve to Grade 1 within 3d OR a biopsy confirms immune-mediated myocarditis.	All Grade 3 myocarditis.	DLT
Myositis/polymyositis	Events that do not resolve to Grade 1 within 30d OR exhibit signs of respiratory insufficiency regardless of optimal medical management	Events that do not resolve to Grade 1 within 30d OR exhibit signs of respiratory insufficiency regardless of optimal medical management	DLT

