In addition to the information presented in the statistical methods section of the protocol (Section 13) which provides the principal features of planned analyses for this study, this SAP provides appropriate statistical analysis methodologies in details. It also documents modifications or additions (if applicable) to the analysis plan that are not “principal” in nature and result from information that was not available at the time of protocol finalization.

PPD Biostatistics and Programming team, designee of Moderna Biostatistics and Programming department, will perform the statistical analysis of the efficacy, safety, pharmacokinetic, and pharmacodynamics; Statistical Analysis System (SAS) Version 9.4 or higher will be used to generate all statistical outputs (tables, figures, listings, and datasets). The SAP will be finalized and approved prior to the clinical database lock for primary analysis. If the methods in this SAP differ from the methods described in the protocol, the SAP will prevail.

2. Study Objectives

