3.2. Study Endpoints

3.2.1. Primary Endpoints

The primary endpoints of the study are as follows:

Phase I

- Incidence and nature of dose-limiting toxicities (DLTs) with mRNA-2416 alone and in combination with durvalumab
- Incidence, nature, and severity of adverse events (AEs)/serious adverse events (SAEs), graded according to the National Cancer Institute (NCI) Common Terminology Criteria for Adverse Events (CTCAE) Version 4.03 for mRNA-2416 alone and in combination with durvalumab

Phase II

- Assessment of objective response rate mRNA-2416 alone and in combination with durvalumab in patients with ovarian cancer based on RECIST v1.1

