9.1.1. Dose-limiting Toxicity

The DLT window of observation will be the first 28 days of mRNA-2416 treatment and meets the following criteria:

- All Grade 3 AEs with the exception of the following:
 - Grade 3 thrombocytopenia lasting <7 days

- Grade 3 neutropenia without fever or lasting <7 days
- Any Grade 4 or Grade 5 toxicity

Death due to disease progression is not considered a DLT.

A summary table of DLTs will be presented, including number and percentage of patients for each PT based on the safety set and will be sorted in descending frequency based on the total of Arm B combining Phase I and Phase II.

All DLT events will be presented in a listing.

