11.6. Statistical Analysis of Pharmacokinetic Parameters

Pharmacokinetic parameters derived from serum concentrations will be individually listed and summarized. The PK parameters with the exception of t_{\max} will display n, mean, standard deviation, CV, geometric mean, median, minimum, and maximum as descriptive statics. However, t_{\max} will only display n, median, minimum and maximum.

For the listings, concentration data will be presented to the same precision as the data is received. All PK parameters will be presented in the listings to 3 significant figures with the exception of t_{\max} , which will be presented to 2 decimal places.

For summary statistics, the following precisions should be used:

- n should be presented to zero decimal places
- CV% should be presented to 1 decimal place
- Mean, standard deviation, geometric mean, median, minimum, and maximum should be presented to the same precision as the listings

12. Interim Analysis

No formal interim analysis is planned.

13. Changes in the Planned Analysis

One of the exploratory endpoints, assessment of the correlation of other investigational serum-based proteins (e.g., anti-drug antibodies) with PK, efficacy, and safety, is not included in this statistical analysis plan.

14. References

Eisenhauer EA et al. New response criteria in solid tumours: revised RECIST guideline (version 1.1). *Eur J of Cancer.* 2009; 45(2):228-247.

DocuSign Envelope ID: B20D66AA-D718-4BD5-9F79-8CFF4FE948CA

Statistical Analysis Plan (SAP) Client Approval Form

Client:	ModernaTX, Inc.
Protocol Number:	mRNA-2416-p101
Document Description:	Final Statistical Analysis Plan
SAP Title:	A Phase I/II, Open-label, Multicenter, Dose Escalation and Efficacy Study of mRNA-2416, a Lipid Nanoparticle Encapsulated mRNA Encoding Human OX40L, for Intratumoral Injection Alone and in Combination with Durvalumab for Patients with Advanced Malignancies
SAP Version Number:	1.0
Effective Date:	29NOV2021
Author(s):	
For PPD: PPD	
For Moderna: PPD	
Approved by:	
PPD	Date (DD-MMM-YYYY)
Biostatistics and programming, PPD	
PPD	Date (DD-MMM-YYYY)
Clinical Development, Moderna, Inc.	
PPD	Date (DD-MMM-YYYY)
Biostatistics, Moderna, Inc.

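### SAP 9.1.1 applies the protocol's Arm A DLT list to both arms, so Arm B's Grade 2 DLTs, two short Grade 3 hematologic DLTs and the relatedness condition are missing from the definition of a Phase I primary endpoint

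*SAP*

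**What the plan says.** Protocol 8.4.2 opens with a condition common to both arms: the event must not be attributable to disease, progression, intercurrent illness or concomitant medication, and must be "at least possibly related to the study therapy". It then defines DLTs separately by arm.

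- **Arm A:** all Grade 3 events with two hematologic exceptions, plus anything of Grade 4 or 5.
- **Arm B:** a 13-row table by type of event, a bullet on related events of Grade 3 or higher, and a hematologic list. The table includes criteria at Grade 2. For myocarditis the Grade 2 cell reads "Events that do not resolve to Grade 1 within 3d OR a biopsy confirms immune-mediated myocarditis".

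SAP 9.1.1 begins "The DLT window of observation will be the first 28 days of mRNA-2416 treatment and meets the following criteria" and reproduces the Arm A list without an arm label. One exception is "Grade 3 neutropenia without fever or lasting <7 days". The table built on it "will be sorted in descending frequency based on the total of Arm B combining Phase I and Phase II", so the list is applied to Arm B. Section 9.1.1 does not refer back to protocol 8.4.2, and no other SAP section defines a DLT.

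The SAP makes this a Phase I primary endpoint (section 3.2.1): "Incidence and nature of dose-limiting toxicities (DLTs) with mRNA-2416 alone and in combination with durvalumab". Its Introduction adds: "If the methods in this SAP differ from the methods described in the protocol, the SAP will prevail". Section 13, on changes to the planned analysis, declares one item only: "One of the exploratory endpoints, assessment of the correlation of other investigational serum-based proteins" (with PK, efficacy and safety).

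**The concern.** With one unlabelled list and a clause that lets the SAP override the protocol, a programmer working from the SAP would classify Arm B events by monotherapy criteria. The protocol's Arm B criteria were written for immune-mediated toxicity of a checkpoint inhibitor combination, where some Grade 2 events are serious enough to limit dose. Appendix E orders a permanent stop for biopsy-proven myocarditis, and for Grade 2 neuromotor syndromes or myositis with respiratory insufficiency. It also orders study drug discontinued for any bullous rash.

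At stake is whether the reported DLT incidence for the combination means what the protocol says it means, and whether it can be reconciled with the dose decisions it is supposed to document.

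**Working it through.** **1. Rows of the Arm B table (protocol 8.4.2).** The rows are diarrhea/colitis, pneumonitis, hepatitis, rash, peripheral neuromotor syndromes, myocarditis, myositis, endocrinopathies, type 1 diabetes, nephritis, amylase/lipase, all other events, and infusion-related reactions: 13 in all. The Grade 2 cell is filled for pneumonitis, rash, neuromotor syndromes, myocarditis and myositis (5) and empty for the other 8. SAP 9.1.1 has no criterion below Grade 3, so all five drop out.

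**2. The two definitions side by side, for an Arm B patient.**

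| Event | Protocol 8.4.2, Arm B | SAP 9.1.1 as written |
|---|---|---|
| Grade 2 non-infectious pneumonitis, still above Grade 1 after 10 days | DLT | not a DLT |
| Bullous rash below Grade 3 | DLT | not a DLT |
| Grade 2 neuromotor syndrome, unresolved at 30 days or with respiratory or autonomic signs | DLT | not a DLT |
| Grade 2 myocarditis, unresolved at 3 days or biopsy-confirmed | DLT | not a DLT |
| Grade 2 myositis, unresolved at 30 days or with respiratory insufficiency | DLT | not a DLT |
| Grade 3 neutropenia with fever above 38.3 °C, under 7 days | DLT | exempt |
| Grade 3 thrombocytopenia with significant bleeding, under 7 days | DLT | exempt |
| Grade 4 neutropenia without fever, 7 days or less | not on the hematologic list | DLT |
| Grade 3 event unrelated to study therapy | not a DLT | DLT |

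The first seven rows are under-counts. The two hematologic ones arise because the Arm B list sets no duration limit for those events, while the SAP exempts by duration alone: its neutropenia exception is joined by an *or*, and its thrombocytopenia exception has no bleeding qualifier. The last two rows are over-counts. The Grade 4 neutropenia row assumes that the hematologic list governs; the bullet on events of Grade 3 or higher, read literally, would count that event if related. The last row applies in Arm A as well.

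**3. Size in one cohort (illustration).** Protocol 8.4.3 and 8.4.4 clear a dose at no more than 1 of 6 patients with a DLT and treat 2 or more as exceeding the MTD.

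- One DLT that the SAP covers plus one that it omits: protocol 2/6 = 33.3%; SAP text 1/6 = 16.7%.
- One true DLT plus one unrelated Grade 3 event in another patient: protocol 1/6 = 16.7%; SAP text 2/6 = 33.3%.

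**4. How often an omitted event might occur.** The documents give no rate. Assuming a combined per-patient probability p for all omitted events, the chance of at least one among 6 patients is 1 − (1 − p)^6:

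- p = 1%: 1 − 0.99^6 = 5.9%
- p = 2%: 1 − 0.98^6 = 11.4%
- p = 5%: 1 − 0.95^6 = 26.5%

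These are chances that a cohort contains an omitted event, not chances of crossing the MTD threshold.

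**5. Secondary: Hy's law in the protocol.** The Arm B hepatitis row sets ALT or AST at 3 × ULN or more with bilirubin at 2 × ULN or more, but places this in the Grade 3 column and leaves Grade 2 empty. Appendix E's Grade 2 bands are ALT/AST above 3 to 5 × and bilirubin above 1.5 to 3 × ULN. A patient at 4 × and 2.5 × therefore meets Hy's law while being Grade 2 on both measures. Appendix E orders a permanent stop for any Hy's law case but prints the order under Grade 3; its Grade 2 row allows treatment to resume.

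**The case against.** The strongest reply is that nothing in practice need go wrong. Protocol 8.4.2 has investigators notify the sponsor of DLTs at once, SAP 9.1.1 promises a listing of all DLT events, and several Arm B criteria (biopsy confirmation, for instance) are hard to derive from grade and date. The table may therefore rest on investigator-reported DLTs. That is plausible, but the SAP does not say so, and the printed definition would still contradict the reports.

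Second, protocol 12.1.1 and 12.2 ask for syndromes rather than separate symptoms. A short febrile neutropenia recorded as a single Grade 3 event would be counted, as would a bleed recorded as its own Grade 3 event. This narrows the hematologic part; it does not touch the Grade 2 part.

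Third, for neuromotor syndromes and myositis one Grade 2 route is non-resolution at 30 days, which may not be known at the 28-day decision. The respiratory and autonomic routes can be.

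Fourth, the omitted events may appear in the adverse-event tables, though not as DLTs.

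A reader might also infer that a wrong MTD could follow. The documents do not support that: under protocol 8.4.1 the safety review committee decides on the escalation rules of 8.4.4, which use the protocol's DLT definition.

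**Conclusion.** The definition in SAP 9.1.1 is wrong for Arm B as written. It omits the Grade 2 criteria in 5 of 13 rows and two short Grade 3 hematologic DLTs (unless the fever or bleed is recorded as its own event of Grade 3 or higher), and it drops relatedness in both arms. The change is undeclared and affects a Phase I primary endpoint. The harm is to reporting: the DLT count may not match the committee's decision at that dose.

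A reader might conclude that DLTs will be under-reported. That does not follow, because the same text also over-counts, and the net direction is unknown. Nor do the documents show that the omitted events will actually be missing from the table, since its source is not stated.

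The contrast of 1/6 with 2/6 is an illustration only. The planned table is by preferred term on the safety set rather than on DLT-evaluable patients, so it need not reproduce the committee's fraction even with correct criteria. The 5.9% to 26.5% range rests on assumed event rates. No claim is made about the expansion stopping rule. The Hy's law ambiguity, and the conflict between the Arm B table and the Grade 3-or-higher bullet, are separate protocol clarifications; the main point does not depend on them.

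**What to change.** In SAP 9.1.1:

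1. Label the present list as Arm A only.
2. For Arm B, carry over the full protocol 8.4.2 definition: table, Grade 3-or-higher bullet and hematologic list.
3. Restore the relatedness condition for both arms.
4. State whether the table uses investigator-reported DLTs or a derivation from adverse-event data.

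This costs one SAP paragraph and brings the SAP back to the protocol. It calls for no redesign and, if investigator reports are the source, no new data.

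Optional, at the next protocol amendment: state that Hy's law, with one pair of thresholds, is a DLT and a permanent stop whatever the grade column, and say whether the Arm B table or the Grade 3-or-higher bullet governs where they differ. The wording is short, but it alters a DLT and a stopping rule. It would need IRB approval before use, as this protocol's earlier amendments did, so it should not delay the SAP correction.

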8.2.1 ARM A DOSE ESCALATION PERIOD

Dose escalation will be conducted using a standard 3+3 study design in order to determine safety and tolerability of the study therapy (see [Section 8.4](#) for further details). The planned mRNA-2416 starting dose is 1.0 mg (0.5 mL) on Day 1 and Day 15 of 28-day cycles. Patients will be evaluated at the end of the first 28-day period (Cycle 1). A sentinel patient will receive their initial dose of mRNA-2416 1.0 mg intratumoral injection per intratumoral injection criteria ([Section 10.1](#)). Following a 7-day observation period, additional patients may be enrolled in the 1.0 mg cohort. [Table 1](#) describes the 1.0 mg starting dose and other dose levels that may be evaluated during this trial. Subsequent dose cohorts may enroll up to 3 patients at a time. No intra-patient dose escalations may occur.

Table 1: Arm A Provisional Dose Levels

Dose level	Proposed mRNA-2416 Q2W dose
-1	0.5 mg (0.25 mL)
1 (starting dose)	1.0 mg (0.5 mL)
2	2.0 mg (1.0 mL)
3	4.0 mg (2.0 mL)
4	8.0 mg (4.0 mL)

Once a dose level has been cleared for safety, the dose level is open to enrollment of up to an additional 9 patients who are willing and eligible to undergo tumor biopsy for analysis (see details in [Section 8.2.2](#)). Any adverse events among patients in the biopsy enrichment cohorts would be considered in determining an appropriate RDE but will not affect the determination of the MTD. These cohorts are only opened at doses cleared for safety and are separate from the 3 + 3 escalation model described in [Section 8.4.4](#).

Patients must have a superficial tumor lesion amenable to injection. A tumor lesion amenable to injection during the Dose Escalation Period is defined as a superficial tumor lesion that is

- clearly visible or palpable
- can be easily injected without the use of imaging guidance, and
- All lesion(s) targeted for the initial injection must be ≥ 0.5 cm on longest diameter, be at least 5 mm thick, and have distinct borders based on exam or imaging, not close to critical structures such as major vessels, nerves, or airways.

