8.4.4 DOSE ESCALATION PROCEDURE

In order to be evaluable for dose determination, a patient must have received $\geq 50\%$ of the planned mRNA-2416 dose and $\geq 75\%$ of the planned durvalumab dose (Arm B) for Cycle 1 and must either have been followed ≥ 28 days following the first dose or have experienced a DLT within 28 days of the first dose. Patients who are not evaluable for dose determination may be replaced.

Dose escalation determination will not occur until the third patient in a cohort has completed their first 28-day study therapy.

- If no patient (0 of 3) in a dose cohort experiences a DLT during the first 28 days, then the next dose cohort of 3 patients will be enrolled at the next dose level per [Table 1](#) following consensus of the SRC.
- If 1 of 3 patients in a dose cohort experiences a DLT, an additional 3 patients will be enrolled in that dose cohort.
 - Provided that no more than 1 of 6 patients in the expanded dose cohort experiences a DLT within 28 days of the first dose, then a dose cohort of 3 patients will be enrolled at the next dose level per [Table 1](#) following consensus of the SRC.
- If ≥ 2 patients in a dose cohort experience a DLT within 28 days of the first dose, that cohort will have exceeded the MTD. No additional patients will be dosed at that level, and 3 patients will be enrolled in the preceding dose cohort, unless 6 patients have already been treated at that dose level. Using the same criteria, lower dose cohorts will be explored as the MTD until ≤ 1 of 6 patients experiences a DLT.

In the event that ≥ 2 of the first 6 DLT-evaluable patients in the 1.0 mg cohort experience a DLT, then the next cohort will be dosed with 0.5 mg mRNA-2416.

In the event that ≥ 2 of the first 6 DLT-evaluable patients in the 8.0 mg cohort experience a DLT, an intermediate dose cohort may be opened at 6.0 mg mRNA-2416.

9 **SELECTION OF PATIENTS**

9.1 **INCLUSION CRITERIA**

All patients must meet all of the following inclusion criteria:

1. Males or females ≥ 18 years of age who have provided written informed consent prior to completing any study-specific procedure
2. Disease state and prior therapies:

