4.3.2. Safety Set

The safety set will consist of all enrolled patients who received any amount of study drug. Patients will be included in the dose cohort corresponding to the dose level which they actually received.

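### SAP 9.1.1 defines and counts dose-limiting toxicities differently from the protocol, so the reported DLT incidence need not match the quantity behind the MTD

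*SAP*

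**What the plan says.** **Endpoint.** SAP 3.2.1, like protocol 7.2, lists "Incidence and nature of dose-limiting toxicities (DLTs) with mRNA-2416 alone and in combination with durvalumab" as the first of two Phase I primary endpoints. The second is the incidence, nature and severity of AEs and SAEs.

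**SAP definition and table.** SAP 9.1.1 opens: "The DLT window of observation will be the first 28 days of mRNA-2416 treatment and meets the following criteria". The criteria are Grade 3 events with two haematological exceptions, plus any Grade 4 or 5 toxicity. That is the protocol's Arm A list, given once for both arms. The table is specified as follows: "A summary table of DLTs will be presented, including number and percentage of patients for each PT based on the safety set". SAP 4.3.2 defines the denominator: "The safety set will consist of all enrolled patients who received any amount of study drug". SAP section 9 groups safety results by treatment arm and dose cohort, with an arm total over both phases.

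**Protocol definition.** Section 8.4.2 requires that the event not be attributed to disease, other illness or concomitant medication, and that it be "at least possibly related to the study therapy and that occurs within the first 28 days of study therapy". It then gives separate criteria for Arm A and Arm B.

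**Protocol counting rules.**
- Section 8.4.4 sets an evaluability rule ("In order to be evaluable for dose determination, a patient must have received"). It requires at least 50% of planned Cycle 1 mRNA-2416 and, in Arm B, at least 75% of planned durvalumab, plus either 28 days of follow-up or a DLT within that time. It adds: "Patients who are not evaluable for dose determination may be replaced".
- Section 8.4.3 sets the MTD at DLTs in fewer than 2 of 6 patients (<33%).
- Section 8.2.7 uses DLT-evaluable patients at the dose level as the denominator of the Expansion DLT rate.
- Section 8.2.1 says of the biopsy-enrichment cohorts: "These cohorts are only opened at doses cleared for safety and are separate from the 3 + 3 escalation model".

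**Precedence.** SAP section 1 says that the SAP overrides the protocol where methods differ. SAP section 13 lists one change from plan, and it is not this one.

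**The concern.** Both halves of the DLT percentage depart from the protocol.

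The numerator has no relatedness test. SAP 9.1 defines an AE irrespective of drug relationship, so a literal programmer would count an unrelated Grade 3 event in the first 28 days. In Arm B it also uses a criteria list different from the one protocol 8.4.2 assigns to that arm.

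The denominator includes anyone who received any drug. A patient who left early without a DLT cannot show that none would have occurred, which is why the protocol treats such patients as replaceable. SAP 4.3 defines four analysis sets, none of them DLT-evaluable, although SAP 3.3 uses that term.

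At stake is whether a reader of the study report can trace a Phase I primary endpoint to the data that set the MTD.

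**Working it through.** **1. The protocol's threshold.** 2/6 = 33.3% and 1/6 = 16.7%. The rule of fewer than 2 of 6 therefore agrees with the stated <33%.

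**2. Non-evaluable patients in the denominator.** The reported rate is d/(n + m), where d is the number of patients with a DLT, n the evaluable patients and m the dosed but non-evaluable patients. The documents give no m, so a small range is shown for d = 2, n = 6:

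| m (assumed) | Rate |
|---|---|
| 0 | 2/6 = 33.3% |
| 1 | 2/7 = 28.6% |
| 2 | 2/8 = 25.0% |

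These figures need a row for patients with any DLT, which SAP 9.1.1 does not state. By preferred term, 2/8 prints only if both patients had the same term. Otherwise there are two rows of 1/8 = 12.5%.

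**3. Mixing study parts.** This is a separate matter from evaluability. Take a cleared Arm A level with 1 DLT in 6 escalation patients. Add up to 9 enrichment patients (protocol 8.2.1) and the minimum of 3 confirmation patients (protocol 8.2.4), with no further DLT. If all share the dose-cohort column:

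- 6 + 9 + 3 = 18
- 1/18 = 5.6%, against 1/6 = 16.7%

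All three parts belong to Phase I, so no pooling with Phase II is needed.

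**4. Dropping relatedness.** The documents give no background rate of unrelated Grade ≥3 events, so q below is an assumption. Assume also a related-DLT rate of p = 10% per patient, with independence. Without the relatedness test, the per-patient probability of a counted event is P = 1 − (1 − p)(1 − q). The chance that at least 2 of 6 patients are counted is 1 − (1 − P)^6 − 6P(1 − P)^5.

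| q (assumed) | P | Chance of ≥2 of 6 |
|---|---|---|
| 0 (relatedness applied) | 0.100 | 0.114 |
| 5% | 0.145 | 0.212 |
| 10% | 0.190 | 0.320 |
| 20% | 0.280 | 0.536 |
| 30% | 0.370 | 0.717 |

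This is the chance that a literal SAP count reaches the protocol's limit in the report. It is not the chance that escalation would have stopped.

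**5. Direction.** Steps 2 and 3 lower the percentage in these examples; step 4 raises it. The effect of using the Arm A list for Arm B cannot be sized from the documents.

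**The case against.** **The protocol itself supports the safety set.** Section 13.4.2 places all safety analyses in the Safety Population, and 13.4.1 defines no DLT-evaluable population. This stands: the denominator follows the protocol's general statistical text. But it conflicts with the specific rules in 8.2.7 and 8.4.4, so the inconsistency lies within the protocol as well. It does not explain the missing relatedness condition or the missing Arm B criteria.

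**No decision rests on the table.** This also stands. The Safety Review Committee sets the MTD during conduct under 8.4.3 and 8.4.4 and documents it in writing. A reader might infer that the MTD or an escalation step would be wrong; the documents do not support that.

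**Listings give traceability.** All DLTs are listed, and SAP section 4 sorts listings by arm, study part and dose cohort. Each DLT can therefore be assigned to its part, but the listing does not supply the evaluable denominator.

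**Most added patients may be evaluable.** Enrichment and confirmation patients can each satisfy 8.4.4, and 8.2.7 does not split by study part. So the 1/18 figure reflects mixed study parts, and a DLT-evaluable set alone would not change it.

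**Phase II pooling is not established.** A reader might add about 30 Arm A Expansion patients and infer 1/48 = 2.1%. SAP section 9 states pooling of phases only for the arm total, so separate phase columns remain a fair reading.

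**The eCRF may carry an investigator's DLT flag that already includes relatedness.** This is possible, but SAP 9.1.1 does not refer to one and gives its own criteria.

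**Conclusion.** The point holds as a reporting and definition inconsistency. Read literally, SAP 9.1.1 yields a DLT incidence that can count unrelated events, applies one criteria list to both arms, and includes dosed but non-evaluable patients. It need not equal the quantity behind the MTD, and the SAP's precedence clause means the protocol does not correct it.

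The size is illustrative. The fall from 33.3% to 25% assumes two replaced patients and an any-DLT row. The fall from 16.7% to 5.6% assumes that 9 enrichment and 3 confirmation patients share the column without a further DLT. The relatedness figures rest wholly on assumed rates.

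A reader might infer that the plan systematically understates toxicity. It does not follow: the numerator and denominator errors oppose each other, and the net bias cannot be signed. The change should be made, but it does not call the dose-finding itself into question.

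**What to change.** - Define DLTs in SAP 9.1.1 by reference to protocol 8.4.2, including relatedness. The single SAP list and the protocol's separate Arm B criteria must be reconciled.
- Add a DLT-evaluable set to SAP 4.3, taken from protocol 8.4.4.
- Report patients with any DLT over evaluable patients, by arm, dose level and study part (3+3 escalation, biopsy enrichment, confirmation, expansion).
- Keep the safety-set table by preferred term as supportive.
- Reconcile protocol 13.4.2 with 8.2.7 and 8.4.4, and record any intended departure in SAP section 13.

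The cost is wording and one derived population flag. Reported DLT percentages may move in either direction.
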